The DLRT for SAD cohort 11 will also make dosing recommendations for cohort 9 ([Figure 1-1 \[A\]](#)). [REDACTED]

Cohort 10 will enroll **up to** 20 subjects and will include the use of [REDACTED]

[REDACTED] Therefore, the dose recommended for cohort 10 should be the same as a dose studied in a previous **MAD** cohort.

[figure not shown]
The dose recommended for cohort 10 will depend on the final dose recommended for cohort 9 and the safety and tolerability profiles for MAD cohorts 7 and 8 ([Figure 1-1 \[B\]](#)). [REDACTED]

[REDACTED]

In all dose escalation process **between cohorts**, DRLM will make a recommendation and Amgen will make the final decision on dose level.

Part C (cohort 12 to 13) is an open-label modified dose-escalation MAD study in subjects with obesity. Doses selected for these cohorts have been doses previously studied in Part A and Part B and have been shown to have an acceptable safety and tolerability profile. Doses selected in Part C will not exceed the dose levels previously studied in the MAD cohorts (420 mg SC Q4Wx 3). Cohort 12 will receive [REDACTED] mg SC on days [REDACTED] followed by [REDACTED] mg SC on days [REDACTED]. Cohort 13 will receive [REDACTED] mg SC on days [REDACTED] followed by [REDACTED] mg SC on days [REDACTED]. Up to 6 subjects per cohort will receive AMG 133 as described in Section 1.3. Cohort 12 and cohort 13 will enroll in parallel. The DLRT will review the safety and laboratory data through at least day 36.

Figure 1-1. Dose Selection for Cohort 9 and 10

- MAD cohorts 7 to 9: Study drug will be administered every 4 weeks for a total of 3 SC doses. The dose levels will be defined after evaluation of the available PK and PD data from preceding cohorts in the SAD phase (Part A). Three different dose levels will be evaluated with the lowest dose administered to cohort 7, and 2 higher ascending doses administered to cohorts 8 and 9. The dose level for cohorts 7 to 9 will not exceed the highest dose evaluated in cohorts 1 to 6 and cohort 11 (Part A). Subjects enrolled in cohorts 7 to 9 will also be asked to [REDACTED]
[REDACTED]
- MAD cohort 10: **Up to** twenty subjects will be randomized in a 3:1 ratio to receive AMG 133 or placebo SC. All subjects will be asked to use [REDACTED]
[REDACTED]

The dose level will be defined after evaluation of the available PK and PD data from preceding MAD cohorts. The dose level will not exceed the highest dose evaluated in cohorts 7 to 9 (Part B).

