Part C: Cohorts 12 - 13: Subjects who meet all the screening inclusion criteria and none of the exclusion criteria will be eligible to report to the research facility once on day -2 (up to day -4), at which time assessments will be performed to confirm eligibility. If subjects are eligible after the completion of all day -2 assessments, subjects will receive AMG 133 on day 1.

Day -1

Part A: Cohorts 1 to 5 and cohort 11: A [REDACTED] test will be performed on day -1 along with additional procedures as outlined in the Schedule of Activities in **Section 1.3.** As part of the [REDACTED]

summarized in the Schedule of Activities in **Section 1.3**. [REDACTED] tests will not be performed in cohort 6.

Part B: cohorts 7 to 10: Subjects who meet all the screening inclusion criteria and none of the exclusion criteria will be eligible to report to the research facility on day -1, at which time assessments will be performed to confirm eligibility. If subjects are eligible after the completion of all day 1 assessments, subjects will be randomized to receive either AMG 133 or placebo on day 1.

Day 1:

Part A: After completion of all predose procedures on the day of dosing (day 1), subjects will receive investigational product (SC for cohorts 1 to 5 and cohort 11 and IV for cohort 6, only). Subjects will undergo vital signs and pharmacokinetics blood draws postdose as outlined in the Schedule of Activities in **Section 1.3**.

Part B: After completion of all predose procedures on the day of dosing (day 1), subjects will receive investigational product (SC for cohorts 7 to 10). Subjects should undergo additional vital sign assessments 3 hours after dosing but are not scheduled to get postdose blood draws on day 1 (see Schedule of Activities in **Section 1.3**).

Part C: After completion of all predose procedures on the day of dosing (day 1), subjects will receive AMG 133 (SC). Subjects are scheduled to get postdose blood draws on day 1 but should undergo additional monitoring (per clinical site standard operating procedures) and vital sign assessments approximately 4 to 5 hours after dosing. The subjects can be discharged from the clinical facility based upon a stable vital signs and assessment per clinical site standard operating procedures.

Day 7

Cohorts 1 to 5 and cohort 11: A [REDACTED] test will be repeated on day 7 along with additional procedures as outlined in the Schedule of Activities in **Section 1.3**.

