Adverse events			X	X	X	X	X	X ⁱ	X	X ⁱ	X
Serious adverse events	X	X	X	X	X	X	X	X ⁱ	X	X ⁱ	X
Concomitant therapies review	X	X	X	X	X	X	X	X ⁱ	X	X ⁱ	X

STUDY TREATMENT											
Amgen investigational product											
LABORATORY ASSESSMENTS											
Coagulation ^j	X	X									
Hematology ^j	X	X		X	X	X	X		X		X
Chemistry ^j	X	X		X	X	X	X		X		X
HS-CRP ^j			X						X		X
HIV, Hepatitis B and C screening ^j	X										
Serum amylase and lipase ^j			X	X	X	X	X		X		X
eGFR ^j	X	X									X
Urinalysis ^j	X	X							X		X
Alcohol, cotinine, and drug screen ^j	X	X									

Page 1 of 2

Footnotes defined on last page of the table.

Table 5. Schedule of Activities – Part C Cohort 12

PROCEDURE	SCREENING		TREATMENT PERIOD							SFU/EOSA		
	Study Day	-28	-2 ^b	1	8	15	20	43	57	71	132	193
Visit Windows							± 1 day		± 3 days		± 7 days	
Visit type	C	C	C	C	C	C	C	P	C	P	C	
Serum and/or Urine pregnancy test (females only) ^j	X	X										X
Serum FSH test ^j (postmenopausal females only)	X											
Anti-AMG 133-antibody ^{k,m}			X ^d		X ^d		X ^d		X			X
STUDY-SPECIFIC ASSESSMENTS (eg, DISEASE-SPECIFIC ASSESSMENTS, RADIOLOGICAL ASSESSMENTS)												
PHARMACOKINETIC ASSESSMENTS												
Plasma AMG 133 pharmacokinetics ^{k,m}				X ^d	X ^d	X ^d		X ^d		X		X
PHARMACODYNAMIC ASSESSMENTS												

PHARMACOGENETIC ASSESSMENTS											
Pharmacogenetic studies ^{o,m}											
IMAGING				X							

Page 2 of 2

BP = blood pressure; C = clinic visit; C-SSRS = Columbia Suicide Severity Rating Scale; cm = centimeters; [REDACTED];
[REDACTED]; ECG = electrocardiogram; eGFR = estimated glomerular filtration rate; EOS = end of study;

FSH = follicle stimulating hormone:

[REDACTED] HIV = human immunodeficiency virus; HR = heart rate; HS-CRP = high-sensitivity C-reactive protein;
[REDACTED] p = phone visit; PD = pharmacodynamic; PHQ9 = Patient Health Questionnaire-9; RR = respiratory rate;
[REDACTED]; SFU = safety follow-up; Temp = temperature.

Please note: Subjects are eligible for an optional in-house residence period on Day 1 and 8 for an overnight observation period. Subjects are eligible for a required in-house residency period for Day 15 and 43. Subjects will receive AMG 133 on Days 1, 8, 15, and 43.

^a Upon permanent discontinuation from the study treatment for any reason, an SFU visit will be performed approximately 30 (+3) days after the end of the last dosing interval of investigational product.

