[REDACTED] All subjects in each Part B (MAD) cohort may be dosed on the same day.

Cohort 10 will enroll **up to** 20 subjects and will include the [REDACTED]

[REDACTED]. Therefore, the dose recommended for cohort 10 should be the same as a dose studied in a previous cohort.

The dose recommended for cohort 10 will depend on the final dose recommended for cohort 9 and the safety and tolerability profiles for MAD cohorts 7 and 8 ([Figure 1-1 \[B\]](#)).

In all dose escalation process, DRLM will make a recommendation and Amgen will make the final decision on dose level.

- MAD cohorts 7 to 9: Study drug will be administered every 4 weeks for a total of 3 SC doses. The dose levels will be defined after evaluation of the available PK and PD data from preceding cohorts in the SAD phase (Part A). Three different dose levels will be evaluated with the lowest dose administered to cohort 7, and 2 higher ascending doses administered to cohorts 8 and 9. The dose level for cohorts 7 to 9 will not exceed the highest dose evaluated in cohorts 1 to 6 and cohort 11 (Part A). Subjects enrolled in cohorts 7 to 9 will also be asked to [REDACTED]
- MAD cohort 10: Up to twenty subjects will be randomized in a 3:1 ratio to receive AMG 133 or placebo SC. All subjects will be asked to use [REDACTED]

[REDACTED] The dose level will not exceed the highest dose evaluated in cohorts 7 to 9 (Part B).

Part C (cohorts 12 to 13) is an open-label modified dose-escalation MAD study in subjects with obesity. Approximately 12 subjects (up to 6 subjects per cohort) will enroll in Part C and receive AMG 133 (see Table 7). Doses selected for these cohorts are known to have an acceptable safety and tolerability profile based on data reviewed by the DLRT from previous cohorts in Part A and Part B and will not exceed the dose levels previously studied in the MAD cohorts 7 to 9. Cohort 12 will receive [REDACTED] mg SC on days [REDACTED] followed by [REDACTED] mg SC on days [REDACTED] Cohort 13 will receive [REDACTED] mg on days [REDACTED] followed by [REDACTED] mg SC on days [REDACTED]. Cohorts 12 and 13 will enroll in parallel. The DLRT will review the safety and laboratory data through at least day 36.

Table 7. Planned Dose Levels by Cohort

	Cohort	No. Subjects	AMG 133/Placebo Dose/ Frequency	Route	N (active: placebo)
Part A	1	8	21 mg day 1	SC	6:2
	2	8	Not exceeding 70 mg day 1 ^a	SC	6:2
	3	8	Not exceeding 140 mg day 1 ^a	SC	6:2
	4	8	Not exceeding 280 mg day 1 ^a	SC	6:2

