4.2.2 Number of Sites

Approximately 1 to 3 investigative sites in United States will be included in the study. Sites that do not enroll subjects within 1 month of site initiation may be closed.

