Part C consists of two cohorts (cohorts 12 and 13), both open-label to evaluate dose-level escalation from 70 mg to 420 mg. The objective of Part C is to evaluate first dose effects of AMG 133 on GI-related adverse events using a titration methodology. Cohort 12 will start at a lower dose [redacted] mg) of AMG 133 given [redacted]

Cohort 13 will start at a lower dose ([redacted] mg) of AMG 133 given [redacted]

The rationale for dose selection for Part C is based on the available PK data from this ongoing FIH study cohorts 1 to 11 (Part A and Part B) and the NOAEL exposures established based on 13-week GLP repeat-dose studies in mouse and cynomolgus monkeys.

Similarly, for cohort 12, the predicted human exposure multiples for intact AMG 133 following the second dose of [redacted] mg on Day [redacted] are approximately 40.5-fold and 45-fold for C_{max} and AUC_{ss} , respectively, based on NOAEL established in cynomolgus monkeys, and 43-fold and 42.4-fold for C_{max} and AUC_{ss} , respectively, based on NOAEL established in mice. The predicted human exposure multiples for total AMG 133 following the second dose of [redacted] mg on Day [redacted] are approximately 45-fold and 49-fold for C_{max} and AUC_{ss} , respectively, based on NOAEL established in cynomolgus monkeys, and 54-fold and 42-fold for C_{max} and AUC_{ss} , respectively, based on NOAEL established in mice (Table 8 and Table 9).

For cohort 13, the predicted human exposure multiples for intact AMG 133 following the second dose of [redacted] mg on Day [redacted] are approximately 39-fold and 43.2-fold for C_{max} and AUC_{ss} , respectively, based on NOAEL established in cynomolgus monkeys, and 41.3-fold and 40.6-fold for C_{max} and AUC_{ss} , respectively, based on NOAEL established in mice. The predicted human exposure multiples for total AMG 133 following the second dose of [redacted] mg on

Day █ are approximately 42.2-fold and 45.5-fold for C_{max} and AUC_{ss} , respectively, based on NOAEL established in cynomolgus monkeys, and 50.9-fold and 47.5-fold for C_{max} and AUC_{ss} , respectively, based on NOAEL established in mice (Table 8 and Table 9).

Table 8. Estimated Exposure Margins of Intact AMG 133 Following Repeat Doses (Q4W)

Clinical Dose (mg)	Route	Predicted Human Exposure		Predicted Exposure Multiples ^a			
		AUC ₀₋₂₈ (μ g·hr/mL)	C_{max} (μ g/mL)	Mouse ^b		Monkey ^c	
█ (cohort 12) ^f	SC	17 731	37	42.4	43	45.1	40.5
█ (cohort 13) ^f	SC	18 513.6	38.5	40.6	41.3	43.2	39

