6.4 Measures to Minimize Bias: Randomization and Blinding

6.4.1 Method of Treatment Assignment

Subjects will be randomized in a 3:1 allocation ratio, to AMG 133 to placebo, respectively, in double-blind manner **in Part A and Part B cohorts 1 to 11 only. Part C cohorts 12 to 13 is an open-label study.**

The randomization will be performed by IRT.

Subjects will be assigned a randomization number based in sequential order in which they qualified to be randomized. Subjects will be considered randomized once a unique subject randomization number has been assigned.

The randomization date is to be documented in the subject's medical record and on the enrollment CRF.

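### Cohorts 12 and 13 enroll in parallel from one population on two titration schedules with no assignment rule; a 1:1 IRT list blocked by site would protect the descriptive side-by-side reading at low cost.

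*Protocol*

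**What the plan says.** Protocol 6.4.1 describes 3:1 randomization of AMG 133 to placebo and applies it "in Part A and Part B cohorts 1 to 11 only. Part C cohorts 12 to 13 is an open-label study". The synopsis (1.1, day -2) says Part A subjects who remain eligible are randomized. The matching Part C sentence has no such step: "If subjects are eligible after the completion of all day -2 assessments, subjects will receive AMG 133 on day 1".

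Protocol 4.1 gives the size and timing of Part C: "Approximately 12 subjects (up to 6 subjects per cohort) will enroll in Part C and receive AMG 133" and "Cohorts 12 and 13 will enroll in parallel". The purpose is in 4.3: "The objective of Part C is to evaluate first dose effects of AMG 133 on GI-related adverse events using a titration methodology".

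The notes to the schedules of activities (1.3) separate the two cohorts. For cohort 12, "Subjects will receive AMG 133 on Days 1, 8, 15, and 43". Cohort 13 is dosed on days 1, 8, 15, 22, 29 and 57. Eligibility (5.1 and 5.2) is a single list. Criteria 241 to 244 name cohorts 12 and 13 together, and no criterion tells them apart. On sites, 4.2.2 says: "Approximately 1 to 3 investigative sites in United States will be included in the study".

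On analysis, Protocol 9.1 states that nothing will be tested. Protocol 9.4.2.1 presents AMG 133 data by cohort and says Part C is summarized separately.

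**The concern.** Ascending-dose cohorts have to run in sequence, so subjects cannot be randomized between them. Cohorts 12 and 13 run in parallel, so that reason does not apply. Calling Part C open-label settles blinding; it does not say how subjects are allocated.

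Two titration schedules reported next to each other invite the question of which was better tolerated. Cohort 12 against cohort 13 is the only concurrent contrast Part C offers, because any comparison with Part B is historical. With no assignment rule, nothing in the plan prevents the schedule from following the site, the order of available places or the investigator's judgement about a subject. GI symptoms are largely subject-reported and Part C is open-label. With so few subjects, an imbalance in who was placed where could not be adjusted for in the analysis.

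**Working it through.** **1. The plan's own figure.** The only sample-size statement is the chance of seeing at least one adverse event among 87 exposed subjects, 1 − (1 − p)^87.
- Exposed: 42 + 18 + 15 + 12 = 87. Enrolled: 56 + 24 + 20 + 12 = 112.
- p = 3%: 1 − 0.97^87 = 92.9%. p = 5%: 1 − 0.95^87 = 98.8%. Both match Protocol 9.2 and SAP 3.2.
- Randomizing between cohorts 12 and 13 changes none of these numbers. No figure is given for cohort 12 against cohort 13.

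**2. Is there an assignment rule?**
- 6.4.1 addresses active against placebo and excludes Part C.
- The N/A for Part C in Table 7 is in the active-to-placebo column, so it does not address cohort 12 against cohort 13.
- 1.1 and 4.1 give parallel enrollment and a maximum of 6 per cohort, and no more. SAP 3.1 repeats this.
- The documents are therefore silent; they do not state a choice.

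**3. What could 6 against 6 show?** One subject is 1/6 = 16.7 percentage points of an observed rate, and two are 33.3 points. This is granularity and would be the same under randomization.
- A two-sided Fisher test reaches 0.05 only at 6 against 1 (p = 0.015), 5 against 0 (p = 0.015) or 6 against 0 (p = 0.002).
- Exact power is 2% for 90% against 60% and 10% for 90% against 45%. The 90% start is the approximate first-dose GI rate reported for cohorts 7 to 10 in Protocol 4.3; the lower rates are assumed.
- An observed 3 of 6 has a 95% Clopper-Pearson interval of 12% to 88%.

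**4. Size of a site effect (assumed rates, not in the documents).** Suppose two sites supply 6 subjects each, record GI events at different rates, and the schedule has no effect. The false difference between cohorts is then:

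| Site mix in cohort 12 / cohort 13 | Sites at 90% and 50% | Sites at 90% and 70% |
|---|---|---|
| 6:0 / 0:6 | 40 points | 20 points |
| 5:1 / 1:5 | 27 points | 13 points |
| 4:2 / 2:4 | 13 points | 7 points |
| 3:3 / 3:3 | 0 | 0 |

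For the 4:2 row: (4 × 0.9 + 2 × 0.5)/6 − (2 × 0.9 + 4 × 0.5)/6 = 0.133.

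**5. What randomization leaves.** Take a trait held by 6 of 12 subjects, split 6:6 without blocking on it.
- P(exactly 3:3) = 20 × 20/924 = 43.3%, so P(4:2 or worse) = 56.7%.
- P(5:1 or worse) = 2 × (36 + 1)/924 = 8.0%.

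Chance imbalance is therefore common. Blocking by site controls it for site, but not for unmeasured proneness to GI events.

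**6. Link to the analysis sets.** Protocol 9.3.1.1 and SAP 6.1 build the full analysis set from randomized subjects, and the safety set is the same set. SAP 5 takes actual treatment group from the randomized group and study exposure from the randomization date. Read literally, these definitions do not cover subjects who were never randomized.

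**The case against.** The strongest reply is that the plan never makes this comparison. No hypotheses are tested, the sample size is practical, and neither document names cohort 12 against cohort 13 as an objective, endpoint or contrast. Protocol 6.2.1 adds that the dose level review team makes no dose-level recommendation from these cohorts because they are terminal. All of this stands, and it confines the point to the descriptive reading.

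A reader might infer that sites steer GI-prone subjects to one schedule. The documents do not show that; they leave it possible. Exclusions for GI conditions affecting motility, recent GLP-1 receptor agonist use, prior AMG 133 exposure and known sensitivity to the class (criteria 206, 224, 225, 230) also narrow the scope for it. The site argument disappears if a single site enrolls Part C, which 4.2.2 allows.

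A reader might also infer that an IRT step would cost nothing and would clear the comparison of site and selection effects. Neither is supported. No document gives an IRT cost, and step 5 shows that chance imbalance remains likely at this size. Open-label reporting bias is untouched.

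What survives is that two concurrent cohorts from one population have no stated assignment method, and a simple one is available.

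**Conclusion.** The point holds as a cheap improvement to the design. It is not a flaw in a planned inference. The effect is confined to the informal comparison of GI tolerability between two cohorts of at most 6, where a difference could arise from subject selection, or from site if more than one site takes part. Under the assumed site rates the false difference could reach 20 to 40 points with complete separation by site, and 0 with balance by site. Those rates are illustrative.

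Randomization would remove systematic selection in expectation. It would not make 6 against 6 precise. The conclusion rests on the absence of any assignment rule in the unredacted text of either document. It does not support a claim that Part C's results are invalid or that steering takes place.

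**What to change.** In Protocol 6.4.1, with matching text in 1.1, 4.1 and SAP 3.1, assign eligible Part C subjects 1:1 to cohort 12 or cohort 13 through the existing IRT. Issue the assignment once eligibility is confirmed (day -2, or up to day -4), in small blocks by site. Keep Part C open-label and its analysis descriptive, and say that the cohorts are not powered for comparison. In an open-label study the last place in a fixed block of two is predictable, so the block sizes should not be disclosed to sites.

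This also makes Part C subjects randomized, as the full analysis set and safety set definitions require.

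The cost is one extra IRT list and some wording. No subjects, visits or procedures are added, and the 112, 87, 92.9% and 98.8% figures are unchanged. The downside is that a subject must consent to either schedule: four or six dosing days, with different residency days.

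If the sponsor prefers not to randomize, the alternative is to state the assignment rule, state that the two cohorts will not be compared, and reword the analysis-set definitions so that dosed Part C subjects are included.

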6.4.2 Blinding

This is a double-blind study **for cohorts 1 to 11**. Treatment assignment will be blinded to all subjects, site personnel, and Amgen as described below.

6.4.2.1 Site Personnel Access to Individual Treatment Assignments

A subject's treatment assignment is to only be unblinded by the investigator when knowledge of the treatment is essential for the further management of the subject on this study or may potentially impact the safety of the subject. Unblinding at the study site for

any other reason will be considered a protocol deviation. It is encouraged that the Amgen Trial Manager be notified before the blind is broken unless the investigator believes that identification of the study treatment is required for a medical emergency. If this is not possible, the Amgen Trial Manager must be notified within 24 hours after breaking the blind. The date and reason that the blind was broken must be recorded in the source documentation.

6.4.2.2 Access to Individual Subject Treatment Assignments by Amgen or Designees

Blinded individuals will not have access to unblinded information until the study is formally unblinded. Amgen staff and their designees involved in the study will not be blinded but will only be given treatment assignments when there is a need to use the information for analysis, discussion, and internal decision making. Access to treatment assignments and other restricted data are described in Amgen standard documents. Unblinded individuals are to ensure unblinding and potentially unblinding information should not be distributed to the investigators or subjects before the study is formally unblinded.

6.5 Treatment Compliance

Investigational product will be administered at the clinic by qualified staff.

6.6 Treatment of Overdose

The effects of overdose of AMG 133 are not known. In case of dosing error, immediate consultation with the Amgen medical monitor is recommended to discuss subject management and prompt reporting of clinically apparent or laboratory adverse events possibly related to the dosing error.

In case of overdose, subjects should be closely monitored for signs and symptoms of adverse events. Pharmacokinetic assessments should be obtained if possible.

Subjects should be monitored closely until any observed signs and/or symptoms revert to normal.

Adverse events should be reported and documented according to instructions available in Section 8.2.3.

